7.5.13. Pregnancy Test

Results of pregnancy tests will be presented in the listing of laboratory results.

7.5.14. Physical Examinations

Physical examination findings will be presented in the listings.

7.5.15. Dosimetry

Analysis of dosimetry data will be the subject of a separate report.

7.6. Procedures for Handling Missing, Unused and Spurious Data

All available efficacy and safety data will be included in data listings and tabulations. No imputation of values for missing data will be performed in the primary analysis.

Subjects who receive the study agent but have no follow-up for safety will not be included when computing incidence of AEs or laboratory toxicities, because their inclusion would dilute the percentages.

Data that are potentially spurious or erroneous will be examined using standard data management operating procedures, prior to database lock and statistical analysis.

Incomplete medication start and end dates are handled as follows: a missing start month is imputed as June and a missing end month is imputed as December. A missing start and end date are imputed as the last day of the month. If only the year is provided, the start date would be imputed as June 30 and the end date would be imputed as December 31. If the assignment of a missing start or end date conflicts with the available reported data, then the assigned dates will be modified. All modifications will be identified in data listings.

For anti-hypertensive medications, if the start year cannot be determined, this medication should be considered a baseline medication unless the end year is present and prior to the first therapeutic dose of iobenguane I 131.

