7.4.1. Primary Analysis: Reduction in Use of Antihypertensive Medication

The primary endpoint for this trial is the proportion of study subjects with a reduction (including discontinuation) of all antihypertensive medication by at least 50% for at least six months or two cycles of iobenguane I 131. The 50% reduction is determined separately for each baseline medication, based on the total daily dose of the antihypertensive medication(s) on the day of the first therapeutic dose.

A benefit duration period is measured by maximum duration as follows. The benefit duration period commences when the subject's medication is reduced to a level below 50% of baseline, and continues until the subject's medication rises above 50% of baseline, until the onset of a new antihypertensive medication of >14 days' duration, or to the last subject date as described in section 7.4.2, Primary Endpoint Calculation. A benefit duration period must begin during the 12-Month Efficacy Phase but may end during the Long-term Follow-up Phase. If the subject discontinues participation in the study before the Month 12 efficacy evaluation, the last date for calculation of the duration of benefit is the date of termination in the study.

For purposes of illustration, the following examples are provided (Month refers to the number of 28-day months after the first Therapeutic Dose).

- Example 1: A subject experiences the clinical benefit from the beginning of Month 2 to the beginning of Month 4, and then again from the beginning of Month 5 to the beginning of Month 12. Since the maximum duration of the benefit was 7 months, the subject is considered a success on the primary endpoint.
- Example 2: A subject experiences the clinical benefit from the beginning of Month 2 to the beginning of Month 4, and then again from the beginning of Month 6 to the beginning of

Month 11. Even though the subject experienced the clinical benefit for a total of 7 months, the maximum duration of the benefit was only 5 months, so the subject is considered a failure on the primary endpoint.

- Example 3: A subject experiences the benefit from the beginning of Month 2 to the beginning of Month 9. At Month 10, the subject receives another anticancer treatment and is discontinued from the study. Since the maximum duration of the benefit was 7 months, prior to discontinuation, the subject is considered a success on the primary endpoint.

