7.4.2. Calculation of the Primary Endpoint

Criteria for Meeting the Primary Endpoint

Subjects must:

1. Receive an Imaging Dose
2. Receive at least one Therapeutic Dose
3. Have a reduction of each pre-therapeutic dosing (baseline) antihypertensive medication $\geq 50\%$ for a minimum of six consecutive months beginning during the 12-Month Efficacy Phase of the study, during which no new, long-term antihypertensive medication is introduced and maintained for longer than 14 days.

Considerations

1. The introduction of a new, transient (i.e., duration ≤ 14 days) antihypertensive medication regimen at any point during the study will not disqualify a subject from being able to achieve the primary efficacy endpoint. Short duration therapy may be instituted to address an acute increase in blood pressure that might be associated with a transient increase in catecholamine release secondary to a variety of factors including tumor cell death. On the contrary, the primary outcome measures chronic control of hypertension necessitated by long term catecholamine secretion by the active tumor.
2. A transient (i.e., duration ≤ 14 days) dose increase over the baseline dose of an existing antihypertensive medication regimen at any point during the study will not disqualify a subject from being able to achieve the primary endpoint. Existing antihypertensive therapy may be increased for a short duration to address an acute increase in blood pressure that might be

associated with a transient increase in catecholamine secretion secondary to a variety of factors including tumor cell death.

3. The introduction of a new, long-term (i.e., duration > 14 days) antihypertensive medication regimen after receiving a therapeutic dose will disqualify a subject from being able to achieve the primary endpoint while the subject is still taking any dose of the new medication. If the new long-term antihypertensive medication is discontinued, the start date for assessment of the primary endpoint is the date when both the new medication is discontinued and the baseline antihypertensive medications are reduced $\geq 50\%$.
4. New long-term antihypertensive medications introduced before Therapeutic Dose #1 is administered are considered part of the baseline antihypertensive medication regimen that must be reduced by at least 50% for achieving primary endpoint.

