5. A long-term (i.e., duration > 14 days) increase in dose over the baseline dose of an existing antihypertensive medication regimen after receiving a therapeutic dose will not disqualify a subject from being able to achieve the primary endpoint if all antihypertensive medications are reduced to a level of 50% or below the baseline dose for at least six consecutive months in duration, since the increase may have been made before a tumor response was obtained. The introduction of a new antihypertensive medication with a duration of >14 days will be considered as the end of a benefit duration period. The start date for the duration of response is the date that the last antihypertensive medication is reduced to the level of 50% or below the baseline dose.
6. The introduction of an antihypertensive medication regimen or increase in existing antihypertensive medication regimen that occurs after the subject has already met the primary endpoint (i.e., had a $\geq 50\%$ reduction of all antihypertensive medications for at least six consecutive months) will not disqualify the subject from achieving the primary endpoint.

Calculation of Duration of Response

The six-month duration of the primary endpoint response begins on the date during the 12-Month Efficacy Phase when all baseline antihypertensive medications have been reduced by at least 50% and any new medications are discontinued (the date post-therapeutic dosing when the reduction of the last antihypertensive medication reduced by at least 50% or the new medication is discontinued) and ends once six consecutive months (i.e., 168 days) duration of sustained $\geq 50\%$ reduction has been achieved, regardless of the phase of the study during which the end date of the response occurs (i.e., 12-Month Efficacy Phase vs. Long-Term Follow-Up Phase).

The end date for which the duration of the $\geq 50\%$ reduction of all antihypertensive medications is determined as the earlier of:

- a. the date that the subject no longer meets the criteria of having a $\geq 50\%$ reduction of all baseline antihypertensive medications (i.e., the starting date of a new long-term continuing antihypertensive medication or a dose change in an existing regimen of antihypertensive medication that exceeds the $\geq 50\%$ reduction of the baseline dose that is greater than 14 days in duration and continues without a reduction to the $\geq 50\%$ level)

OR

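### SAP 7.6 dates a day-missing antihypertensive start at month-end, which can flip a near-threshold responder call, and no planned analysis tests it (minor)

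*SAP*

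**What the plan says.** **The date rule (SAP 7.6).** For starts and stops alike, "A missing start and end date are imputed as the last day of the month". The only provision specific to antihypertensives concerns a start year that cannot be determined. There is an override: "If the assignment of a missing start or end date conflicts with the available reported data, then the assigned dates will be modified". It gives no replacement date and names no records to check against, though modifications are to be flagged in listings. The same section also says "No imputation of values for missing data will be performed in the primary analysis", without saying whether medication dates are covered.

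**How the dates enter the primary endpoint (SAP 7.4.1 and 7.4.2).** Response needs 168 consecutive days with every baseline antihypertensive cut by at least half.
- Start of benefit: "A benefit duration period must begin during the 12-Month Efficacy Phase but may end during the Long-term Follow-up Phase".
- New drugs: "The introduction of a new antihypertensive medication with a duration of >14 days will be considered as the end of a benefit duration period".
- Increases: the period also ends at "a dose change in an existing regimen of antihypertensive medication that exceeds the" 50% reduction level for more than 14 days.
- Short courses: a new transient (14 days or less) "antihypertensive medication regimen at any point during the study will not disqualify a subject from being able to achieve the primary efficacy endpoint".
- Restart: "If the new long-term antihypertensive medication is discontinued, the start date for assessment of the primary endpoint is the date" on which the new drug has stopped and the baseline drugs are at the reduced level.

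**The 50% threshold.** SAP 7.4.1 opens a benefit period when the dose falls below 50% of baseline. SAP 7.4.2 and protocol 13.3.2.1 also count exactly 50%.

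**Sensitivity analyses (SAP 7.9).** The first requires the six months to be completed inside the 12-month efficacy period. The second counts as a non-responder any subject who begins a new antihypertensive that continues for at least 14 days.

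**The concern.** The start date of a new or increased antihypertensive does two jobs. It closes the benefit period, and with the stop date it decides whether the course is short enough to ignore. Placing a day-missing start at month-end moves it later or leaves it unchanged. If the drug is ongoing, or its known stop falls on or after the imputed start, the measured benefit can only lengthen and the measured course can only shorten. A subject short of 168 days can then be counted as a responder.

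These dates define responders in an open-label, single-arm trial whose success rule is a count against a fixed 10% bound. The planned analyses would not show whether any responder depends on an imputed day.

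**Working it through.** **Inputs.** 168 days (SAP 7.4.2; 6 × 28 under SAP 7.0); the 14-day rule (7.4.2); month-end dating (7.6); n = 58, null 0.10, alternative 0.25, one-sided 0.025, power 0.90 (SAP 6); Agresti-Coull lower bound above 0.10 (7.4.1). Assumption: the true day is equally likely to be any day of a 365-day year (seven months of 31 days, four of 30, one of 28).

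**1. The plan's own figure.** n = [(1.960 × √(0.10 × 0.90) + 1.282 × √(0.25 × 0.75)) / 0.15]² = 58.06, which matches 58.

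**2. Lateness.** With m days in the month and true start day s, lateness is m − s, from 0 to 30. The mean is Σ m(m − 1)/2 ÷ 365 = (7 × 465 + 4 × 435 + 378)/365 = 5373/365 = 14.7 days.

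**3. The 168-day rule.** A true benefit of D days counts as 168 or more if m − s ≥ 168 − D. The share of end dates is Σ max(0, m − (168 − D))/365.

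| True D | Misread as 168 or more |
|---|---|
| 137 | 0 |
| 138 | 7/365 = 2% |
| 140 | 29/365 = 8% |
| 150 | 149/365 = 41% |
| 160 | 269/365 = 74% |
| 167 | 353/365 = 97% |

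Example: benefit starts on 1 October, and one baseline drug is raised above half its baseline dose in March, day unknown, and kept there. Dated 31 March, the benefit is 181 days. The true value is 151 to 181 and is below 168 if the change fell on 1 to 17 March (17 of 31 days). The second 7.9 analysis does not reach this case because no new drug is involved.

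**4. The 14-day rule, stop date known.** A true course of T days, counting both ends, is read as T − (m − s). It is misread as 14 days or less when T − 14 ≤ m − s ≤ T − 1.
- T = 20: 14 start days in each of 12 months, 168/365 = 46%. In a further 125/365 (34%) the stop precedes the imputed start and the override applies.
- T = 30: 166/365 = 45%.
- T = 40: 53/365 = 15%.
- T = 44: 7/365 = 2%.
- T = 45: none.

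**5. The opposite direction.** A day-missing start of a reduced dose is also dated late. A true D then counts as under 168 if m − s ≥ D − 167: 353/365 at D = 168, 7/365 at D = 197, none at 198. A day-missing stop lengthens a course: with a known start, a true 10-day course reads as over 14 days for 305 of 365 stop days.

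**6. What a dated record does.** Suppose a visit on the 15th of a 31-day month. A drug started on days 1 to 15 is on that visit's list, which contradicts month-end. Starts on days 16 to 31 are at most 15 days late. A true 150 days needs 18 days of lateness, so it cannot be misread. A true 160 days needs 8, so it is misread for days 16 to 23, 8 of 31 (26%). The shares in steps 3 and 4 are therefore maxima.

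**7. The success rule.** At n = 58 the Agresti-Coull lower bound is 0.1076 for 11 responders and 0.0944 for 10. The Full Analysis Set size is not given; the cut-off runs from 11 at n = 58 to 13 at n = 75. The chance of exactly 11 of 58 is 7% at a true rate of 0.25 and 13% at 0.19.

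**The case against.** Several objections stand.

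- **Records limit the date.** Protocol 11.5.3 and 11.5.12 have the medication list reviewed at each visit, and 11.5.13 requires a blood pressure reading at every antihypertensive change. Partial dates may be few, and many could be narrowed. However, 7.6 does not tell the analyst to use these records. They are also sparsest where they matter: a benefit of at least 138 days starting after Day 30 ends after Day 168 (30 + 138). From then, unless the second dose was delayed, staff readings fall from weekly to monthly, and follow-up visits are six-monthly.
- **Safeguards exist.** The first 7.9 analysis limits reliance on follow-up dates. The second handles new drugs whose imputed course is at least 14 days. The 7.4.1 listing shows the dates and doses behind each response. But both analyses use the imputed dates. Neither reaches a dose increase misdated within the 12-month period or a long course misread as under 14 days.
- **A late date need not change the call.** The subject must have no other qualifying 168-day window, and stopping a new drug restarts the clock. The example in step 3 also assumes that the increase has its own record with a partial start; if the lower-dose record has a known stop, the override may apply.

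A reader might infer that the rule tilts the trial towards success. The documents do not support that: step 5 shows errors against response from the same rule. When the stop precedes the imputed start, the unspecified modification can go either way. A true course of 10 to 21 March (12 days) moved to 1 March becomes 21 days. A reader might also note that the exact one-sided type I error at n = 58 would rise from 0.027 to 0.060 if one non-responder were always counted as a responder. Nothing in the documents shows that this happens even once.

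**Conclusion.** The point holds, and it is minor. Month-end dating can turn a true benefit of 138 to 167 days into 168 or more, or a true course of 15 to 44 days into 14 or less, under the stated conditions on the stop date. The shares (41% at 150 days, 46% for a 20-day course) assume uniform days and no dated record limiting the start. The number of partial dates, the number of changed calls and the net direction cannot be obtained from the documents. One record decides the trial only if the responder count sits on the cut-off.

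The shortcoming is that no planned analysis tests the imputation and the override has no stated rule. On the no-imputation sentence, the natural reading is that the specific date rule governs, but the SAP should say so.

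The 50% contradiction is separate and certain. Taken literally, a subject whose every drug is exactly halved never enters a benefit period under 7.4.1 but does under 7.4.2. It would be too much to say that such subjects will be lost: 7.4.1 itself defines response as a reduction of at least 50% and refers to 7.4.2 for the calculation.

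**What to change.** 1. In SAP 7.6, bound each partial antihypertensive date first with the visit medication lists and the blood pressure readings taken at each change. Use the same bounds when a conflict forces a modification.
2. In SAP 7.9, add an analysis that recomputes the primary endpoint with partial antihypertensive dates set to the values least, and then most, favourable to response within those bounds. Report how many subjects have an imputed antihypertensive date and how many change responder status.
3. In 7.6, state that the no-imputation sentence does not cover medication dates.
4. In 7.4.1, change below 50% to at or below 50%. In 7.9, align at least 14 days with the more-than-14-days rule of 7.4.2.

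Do not make the earliest possible date the primary rule. With a known stop and no bounding record, a true 10-day course would read as s + 9 days, over 14 whenever s ≥ 6. That is 365 − 12 × 5 = 305 of 365 start days (84%), and it would defeat the allowance for transient courses in 7.4.2.

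Cost: SAP wording, some derivation code and one table. No new data are needed.

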7.7. Procedures for Handling Dose and Dosing Frequency (Anti-hypertensive and Pain Medications)

In order to standardize the reporting of doses and dose frequency, all unique values of these fields from the raw concomitant medication dataset will be exported to an Excel spreadsheet where the total daily dose will be added to create a coded dataset. The Excel sheet will be prepared by the Sponsor and used in the creation of analysis datasets. This standardization will be applied to medications identified as anti-hypertensive medications on the CRF and, separately, to medications identified as analgesics with indications for pain relief

7.8. Subgroup Analyses

The following subgroups will be used for selected analysis including primary and additional efficacy analyses, overall survival and treatment-emergent adverse events:

- Number of therapeutic doses (0, 1 or 2).
- Baseline factors, such as location of metastases (lung and/or liver vs no lung or liver metastases).
- Any prior MIBG/Azedra treatment (yes or no) as recorded in the cancer history case report form.

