9.3 Study Duration

Subjects will attend study visits from the time of signed informed consent through 12 months (efficacy portion) and a 5 year follow-up period after the first Therapeutic Dose of Ultratrace iobenguane I 131. Subjects will be monitored for AE/SAE and Adverse Events of Special Interest (including post radiation toxicity) as described in Section 12. Subjects may undergo additional assessments to confirm response, or as part of institutional standard of care during long-term follow-up. Figure 1 outlines the study period; a more extensive summary of study procedures is given in the Schedule of Procedures (Appendix VII).

FIGURE 1: STUDY DURATION

Signed informed consent, subject enters study Eligibility/dosimetry study Imaging Dose (3 to 6 mCi) of Ultratrace iobenguane I 131 administered within 30 days of first therapeutic dose followed by three I 131 whole body scans to confirm uptake and to determine dosimetry First Therapeutic Dose of Ultratrace iobenguane I 131 administered day 0 I 131 scan within seven days post first therapeutic infusion to assess biodistribution Safety visit 6 weeks post-first Therapeutic Dose Objective tumor response assessments 3 months post-Therapeutic Dose and prior to the second Therapeutic Dose Second Therapeutic Dose Ultratrace iobenguane I 131 administered starting at month 3, at least 12 weeks after the first Therapeutic Dose. I 131 scan within seven days after second Therapeutic Dose Safety visit 6 weeks post second Therapeutic Dose Tumor response assessments, tumor markers (every two weeks through week 24 and monthly from month 7-12), physical exam at months 3 (prior to the second Therapeutic Dose, if administered), 6, 9 and 12 Subject completes regularly scheduled study visits at month 12 Long-term follow-up for adverse events of special interest, overall survival, tumor markers and disease status (inc. clinical benefit) through year 5

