10.2 Dose Modification

Dosimetry will be calculated to confirm that the protocol-specified two administrations of 500 mCi (or 8 mCi/kg for subjects weighing 62.5 kg or less) of Ultratrace iobenguane I 131 does not exceed the specified absorbed dose levels (23 Gy to the kidney, 17.5 Gy to the lungs and 30 Gy
to the liver) over the entire treatment (two therapeutic doses). Additionally, subjects must have recovered from treatment side effects experienced during the initial dose and prior to administration of the second dose. Dose modification, if required, may be based on subject's body weight, estimated renal, hepatic or lung absorbed dose or hematological toxicity. Similarly, the Principal Investigator or designee may modify second dose scheduling, in consultation with the study medical monitor, due to medical condition and/or other logistic or personal reasons. In any case this delay of second therapeutic dose should not exceed 24 weeks from the first therapeutic dose. Specifically, if the total dose requires downward adjustment resulting from the dosimetry calculation, then both the first and second Treatment Doses will be decreased equally.

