10.2.2 Dose modification for hematologic toxicity

The subject's hematologic values must return to baseline levels prior to administration of the second Therapeutic Dose. The administration of the second Therapeutic Dose may be delayed for up to 4 - 12 weeks (i.e., 16 - 24 weeks following administration of the first Therapeutic Dose) to allow for adequate hematologic recovery. If recovery to baseline levels has not occurred within 24 weeks following the initial Therapeutic Dose, the subject should be discontinued from the study.

Additionally, if the subject has experienced:

- Febrile neutropenia (temperature \geq 38.5° C and ANC <1,000/µL); or
- CTCAE Grade 3 thrombocytopenia with active bleeding; or
- CTCAE Grade 4 hematological toxicity >1 week duration at any time following administration of the initial Therapeutic Dose,

The second Therapeutic Dose should be decreased to 425 mCi (or 7 mCi/kg for subjects weighing less than 62.5 kg).

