- b. the date of the subject's last applicable recorded study-related disposition date. If the subject has discontinued the study prior to the end of the 12-Month Efficacy Phase due to any of the following reasons:
- Withdrew consent
 - Was lost to follow-up
 - Death
 - Withdrew due to progressive disease
 - Received other anticancer therapy
 - Experienced an adverse event resulting in study discontinuation

The last participation date is the corresponding disposition date within the 12-Month Efficacy Phase (i.e., date that the subject withdrew consent, was lost to follow-up, died, withdrew due to disease progression, received other anticancer therapy, or experienced an adverse event resulting in study discontinuation).

If the subject has completed the 12-Month Efficacy Phase but continues to meet the criteria of having a $\geq 50\%$ reduction of all antihypertensive medications, the last applicable disposition date would be the long-term follow-up completion/discontinuation date.

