7.4.11. Overall Survival

Overall survival (OS) is defined as the time from the date of first therapeutic dose to the date of death from any cause. OS time will be censored at the last date the subject is known to be alive. The Kaplan-Meier predicted survival rates at Years 1-5 will be reported. Overall survival will be listed and Kaplan-Meier curves will be prepared. The last date that the patient was confirmed to be alive will be obtained from information reported by the clinical site: if this information is collected outside of the CRF the last date the subject is known to be alive or date of death reported from the site will be provided in a spreadsheet and integrated into analysis datasets.

Overall survival will also be presented by primary endpoint status.

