7.5.1. Adverse Events

TEAEs are defined as AEs whose onset dates are on or after the first administration of any amount of study drug to the end of 15 weeks after the administration of the last therapeutic dose of iobenguane I 131. If the onset date is incomplete, then assessment will be made based on available information (i.e., comparing available onset month and year). If the onset date is incomplete and assessment could not be made based on the available information (for example, year is missing) then the AE will be considered as TEAE. Events that resolve prior to date of the first dose of study drug will not be considered as TEAEs regardless of completeness of the onset date. In all table summaries, only TEAEs will be presented. All AEs will be presented in listings, regardless of whether they are treatment-emergent.

All adverse events that are neither serious adverse events nor adverse events of special interest reported with start dates on or after the first day of week 16 following the last therapeutic dose will be presented in a summary table and will be included in the listing of all adverse events.

For subjects who discontinue participation in the study due to receiving another anticancer therapy, all adverse events reported with start dates after the initiation date of the new therapy but prior to the last day of week 15 after the last therapeutic dose will be summarized separately. These events will also be included in the overall adverse event summaries. These events will be flagged in the listings of adverse events.

AEs were originally coded according to system organ class and preferred term using MedDRA version 12, and were recoded to MedDRA version 19.1 for analysis. The AE terms were graded for severity according to the Common Terminology Criteria for Adverse Events v3.0 (CTCAE v3).

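### SAP 7.8 uses number of therapeutic doses received as a subgroup; it is fixed after baseline, so its splits of response, survival and TEAEs are biased even if the second dose does nothing

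*SAP*

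**What the plan says.** SAP 7.8 introduces its list with "The following subgroups will be used for selected analysis including primary and additional efficacy analyses, overall survival and treatment-emergent adverse events". The first entry is "Number of therapeutic doses (0, 1 or 2". The other two, location of metastases and prior MIBG treatment, are baseline factors.

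The timing and conditions of the second dose are in the protocol:

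- Protocol 9.3 has it "administered starting at month 3, at least 12 weeks after the first Therapeutic Dose". Protocol 10.2 sets the outer limit: "In any case this delay of second therapeutic dose should not exceed 24 weeks from the first therapeutic dose".
- Protocol 10.1 makes the second dose depend on hematologic status after the first. Under Protocol 10.2.2, if counts have not recovered by week 24, "the subject should be discontinued from the study".
- Protocol 9.7 also discontinues subjects for progression, another anticancer therapy, or an adverse event leading to discontinuation.

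The outcome definitions that interact with this are in the SAP:

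- Section 7.4.2 requires 168 consecutive days of benefit. For a subject discontinued within the 12-month phase it ends benefit at the disposition date. The listed reasons include death, other anticancer therapy and "Withdrew due to progressive disease".
- Section 7.4.11: "Overall survival (OS) is defined as the time from the date of first therapeutic dose to the date of death from any cause".
- Section 7.5.1 counts TEAEs from the first administration of any study drug "to the end of 15 weeks after the administration of the last therapeutic dose of iobenguane I 131".

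Neither 7.8 nor 7.4.11 gives a landmark, a time-dependent definition of dose number, or a caution on interpretation.

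**The concern.** A subgroup should be fixed before the outcome begins to accrue. Dose number is not: to be counted in the two-dose group a subject must be alive, still in the study and hematologically recovered 12 to 24 weeks after the first dose. Subjects who die, progress or fail to recover early fall into the one-dose group because of that outcome.

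Three results are affected: survival (time guaranteed alive), the primary endpoint (follow-up cut short by the same events that prevent the second dose) and TEAEs (an observation window that lengthens with each dose). The primary objective in SAP 4.2 concerns up to two doses, so a reader may take a one-versus-two display as evidence on the second dose.

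**Working it through.** SAP 7.8 states no figure to reproduce. The inputs are the plan's time limits plus assumptions, marked as such. All calculations assume the second dose has no effect.

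**1. Overall survival.** Take exponential survival with one hazard for everyone, the second dose at day 84 (12 × 7) if alive, and a share q of survivors missing it for unrelated reasons. The documents do not give q; 10% and 20% are assumed. Let S be the probability of surviving to day 84 and C the probability of surviving from day 84 to one year.

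- Two doses: one-year OS = C.
- One dose (deaths before day 84 plus the share q of survivors): one-year OS = q·S·C / (1 − S + q·S).

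The second is below the first whenever any deaths occur before day 84, so the direction does not depend on the inputs.

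Median 24 months (Protocol 7.1 says survival is often 24 months or less): S = 0.5^(84/730.5) = 0.923 and C = 0.5^(281/730.5) = 0.766. With q = 0.10, one-dose OS = 0.1 × 0.923 × 0.766 / (0.077 + 0.092) = 42%. With q = 0.20 it is 0.141/0.261 = 54%. The other rows follow in the same way.

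| Survival assumption | Dead by week 12 | Two doses | One dose, q = 10% | One dose, q = 20% | False gap (points) |
|---|---|---|---|---|---|
| Median 24 months | 7.7% | 77% | 42% | 54% | 22–35 |
| Median 36 months (assumed) | 5.2% | 84% | 54% | 66% | 18–30 |
| 5-year OS 64% (carrier-added series of 50 patients, Protocol 7.2) | 2.0% | 93% | 77% | 85% | 9–16 |

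**2. Primary endpoint.** The non-recovery limit is 24 × 7 = 168 days, equal to the required benefit duration. A subject whose disposition date is day 168 can respond only if benefit began at about day 0. A subject discontinued earlier cannot respond.

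A simulation of 400,000 subjects per scenario gives the scale. It assumes 55% latent responders, onset uniform over days 14–365, mean benefit duration 600 days, and the second dose uniform over days 84–168. With 20–35% progression within a year driving discontinuation, response is 27–34% with two doses and 3–7% with one. With only death and 20% random non-receipt, it is 34% and 20%.

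**3. TEAEs.** Counted from the first therapeutic dose, the window is 15 weeks for one dose and 12 + 15 = 27 to 24 + 15 = 39 weeks for two. The ratios are 27/15 = 1.8 and 39/15 = 2.6. The window actually opens at the Imaging Dose, which may be up to 30 days (4.3 weeks) earlier. Adding that to both groups gives 31.3/19.3 = 1.6 and 43.3/19.3 = 2.2, so the range is about 1.6–2.6.

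At a constant event rate, a 30% one-dose incidence becomes 1 − 0.7^1.62 = 44% at the low end and 1 − 0.7^2.6 = 60% at the high end.

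For toxicity that withholds the second dose the direction reverses. Assume 20% have severe hematologic toxicity and 30% of those do not recover. Among those not withheld for it, incidence is (0.20 × 0.70)/(1 − 0.06) = 15%. With progression, death and 5% random non-receipt added, the simulation gives 15% with two doses and 31% with one.

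**4. Level 0.** These subjects are outside the Full Analysis Set (SAP 5.3), cannot meet the endpoint (SAP 7.4.2, criterion 2) and have no OS start date. Their TEAE window has no defined end.

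**5. What a landmark repairs.** Take subjects alive at day 168, classified by doses received by then (median 24 months, 35% progression at one year). If progression does not affect survival, two-year OS moves from 56% vs 36% to 59% vs 59%. If progression doubles the death hazard and some subjects are withheld for toxicity, it moves from 49% vs 24% to 51% vs 41%.

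**The case against.** The strongest reply is that nothing confirmatory depends on this. SAP 7.8 specifies no test or contrast, the table list in SAP 11 names no table by number of doses, and trial success rests on the Full Analysis Set confidence interval. All of that stands, and it limits the point to the subgroup displays. It does not make those displays interpretable.

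The survival sizes are also assumption-driven. Inclusion criterion 9 requires an expected survival of at least six months, so early deaths may be fewer than a 24-month exponential implies. This is why the range extends down to 9 points.

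A reader might infer more than the documents support:

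- That all one-dose subjects must fail. Those who miss the second dose without being discontinued can still accrue 168 days. A non-recovery disposition may also be dated after day 168. The documents do not say what share of one-dose subjects would be discontinued early.
- That two doses will always look more toxic. This holds for overall incidence, not for dose-limiting hematologic toxicity, and SAP 7.5.5 singles out hematologic events.
- That any difference seen must be artefact. The calculation assumes no dose effect; it shows that the displays could not tell one from bias.

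The zero level causes no conflict in the planned OS table, which is on the Full Analysis Set, and it may have a use for TEAEs.

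**Conclusion.** The point holds for the subgroup displays. Dose number is partly an outcome of the first 12 to 24 weeks, and splitting by it favours two doses on survival and response with no dose effect. The false one-year OS gap is about 9 to 35 points, assuming exponential survival, the second dose at week 12 and 10–20% unrelated non-receipt. For the primary endpoint, failure is built in only for one-dose subjects discontinued before day 168, and very nearly so for those discontinued at it; the simulated sizes rest on assumed onset and progression. The TEAE window ratio of 1.6–2.6 follows from the plan's own time limits and inflates overall incidence, with the opposite bias for hematologic toxicity that withholds the second dose. The Full Analysis Set primary analysis and its success criterion are untouched.

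**What to change.** - **Primary endpoint:** remove number of doses from the subgroups. At minimum, label the split descriptive and state that no dose effect is inferred; this keeps the information on single-dose responders.
- **Level 0:** drop it for efficacy and OS.
- **OS:** show it by number of doses only from a landmark at week 24 after the first dose, the latest permitted second dose, among subjects alive then. State that this removes guaranteed survival time but not selection on progression or toxicity.
- **TEAEs:** tabulate by dosing period (imaging to first dose, first to second dose, after second dose), with the subjects entering each period as denominator. State when the window ends for subjects who never receive a therapeutic dose.

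The cost is SAP wording and some reprogramming. Deaths before week 24 drop out of one descriptive OS display; they remain in the overall OS analysis.
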